5.0 Study Procedures

The intervention period will last 3 months. The baseline outcome assessment will be conducted in person or virtually (via Microsoft Teams or over the phone) and in a private space. All other outcomes will be completed in person, virtually, or mailed. If the interview is completed in person or on the phone it will occur in a private space. *Upon approval of the June 27, 2022 (A033) amendment, the study team will no longer complete 6-month interviews for participants who enroll after this date.* The length of follow-up and schedule of outcome assessments at 1, 3, and 6 months (6-months pre A033 only) (see table 2 below) are to detect three types of treatment effects: 1) "early response" (at 1 month); 2) immediate post-intervention benefits at 3 months; and 3) sustained effects at 6 months post-randomization (3 months post-intervention). Study subjects (Veterans) will be reimbursed \$25 per completed outcome assessment (with 4 scheduled assessments each (baseline, 1, 3, and 6 months). Completion/payment of 6-month interviews will be for those enrolled prior to A033 approval only.

Table 2: Outcome Assessment Protocol: Measures and Schedule of Administration

Domain	Measure	Items	Time (min)	Schedule			
				BL	1 mo	3 mo	6 mo
Covariates	Demographics; disability compensation, comorbidity;	36	10	X			

	range of motion, treatments, BMI, medication list						
Neck pain disability	Neck Disability Index	10	3	X	X	X	X
Pain Severity	Brief Pain Inventory	10	3	X	X	X	X
Pain Interference	PROMIS—pain	4	1	X	X	X	X
Psychological	PHQ-9 Depression	9	2	X		X	X
	PROMIS-Depression	9	2	X		X	X
	GAD-7 Anxiety	7	2	X		X	X
	VA PTSD Screener	4	1	X		X	
	PTSD-PCL-17 (if screen positive)	17	5	X		X	
	Stress	10	3	X		X	
Generic HRQL	Medical Outcomes Study VR-36	36	10	X	X	X	X
Sleep	MOS Sleep Scale	12	3	X		X	
Somatic	Somatic Symptom Scale-8	8	3	X		X	X
	SSD-12	12	4	X		X	X
Pain beliefs	Pain Catastrophizing Scale	13	3	X		X	
Social support	Social Support Scale	12	2	X		X	
Treatment satisfaction	Pain-specific satisfaction	3	2		X	X	X
Intervention credibility	EXPECT Questionnaire	4	2	X		X	
Perceived Response	Global Impression of Change	1	1	X	X	X	X

Therapist-treated massage

Participants randomized to the therapist-treated massage (TT-M) arm will receive a standardized Swedish massage protocol tailored to chronic neck pain as used in [name] studies. We chose a Swedish massage protocol because they are the most widely taught and

practiced massage techniques, well defined procedurally, and safe when administered. Massage therapists will deliver the massage protocol to participants. To facilitate scheduling, improve convenience for therapists and patients, and standardize the TT-M treatment, all sessions will be delivered at approved sites at the VA or in [name]. The massage therapists will use the standard massage techniques applied to the neck region and associated trigger points. Massage sessions will involve a maximum of 60 minutes of hands-on, table time and occur up to twice a week (a frequency which balances practicality and efficacy) for 3 months. During the first massage session, the massage therapist will provide an introduction and overview of massage. A medical history with relevant diagnoses will be pulled from the patient's medical record so the massage therapist will be aware of any issues they might have to work with or around. Thereafter, therapist-treated massage will involve a standardized sequence: 1) hands-on assessment; 2) Swedish massage techniques (e.g. effleurage, pétissage, compression) applied directly to the neck and associated trigger points; and 3) identification and treatment of compensatory patterns. While massage therapists will be permitted to use the range of Swedish massage techniques in the protocol, we will discourage them from providing self-care recommendations about postures, behavioral changes, and sleep.

Therapist-treated massage intervention: adherence

To track adherence to TT-M, we will record attendance at massage sessions. Veterans will be encouraged to call study staff if any problems arise. As above, we will define adequate adherence as completion of at least 75% (18) of massage therapy visits. Adherence will be considered as a potential moderator of treatment effect.

We acknowledge the tension between individualizing treatment which is patient-centered and aims to best help patients and standardizing to facilitate reproduction. First, massage sessions will be delivered by therapists with experience in treating neck pain and will enable therapists to develop and provide individualized treatments within a standardized protocol framework. Second, all therapists who participate will receive a training workshop from [name] to emphasize standardization of techniques used within specified timeframes of treatment intent. Third, the therapists will document treatment delivery details (techniques, time) with online, REDCap forms which will also assist with fidelity measures. Finally, in an effort to address fidelity concerns with multiple therapists adhering to the therapist delivered massage protocol framework, each study massage therapist trained and scheduled participants will have delivered sessions randomly observed and assessed by a massage assistant with the developed fidelity checklist (attached). We will randomly observe each therapist's delivered sessions.

Co-interventions

The massage intervention will complement usual care and standard medical treatments for chronic neck pain. We will assess whether TT-M participants continue massage beyond the active intervention period (e.g., 3 months) for those who enroll prior to approval of A033. Participants in all study arms will continue to be followed by their treating physicians/providers for all medical care unrelated to the trial. This includes continuation of other medications as prescribed, clinic visits, and other care as usual. Specifically, use of medications, and specialist consultations (rehabilitation, pain clinic, and orthopedics) for neck pain will be permitted (and assessed), both to adjust for co-intervention differences between arms in the analyses.

Waitlist Control Arm

Participants in the control arm will undergo outcome assessments on the same schedule (baseline, 1, 3, and 6 months) as the treatment group. Six month interviews will only be completed for participants who enroll prior to approval of A033. Participants in the waitlist

control will be instructed to continue their medical care as normal and to not begin any massage treatment during the 3-6 months of the study (dependent on enrollment date). At the completion of the final 6-month outcome (pre A033 approval) or 3-month outcome (post A033 approval) participants in the control arm will be eligible to attend a massage self-care training session with [name]. Those enrolled prior to the approval of A033 will also be offered an incentive massage to be completed by a study massage therapist.

Emailing Participants

The TOMCATT Team will utilize Azure RMS – an encryption system approved for email communication with Veterans by the VA nationally – to communicate with study participants. The TOMCATT team will use Azure RMS for consent/enrollment purposes and will use Azure RMS to email participants about their massage schedule and follow-up interviews, when needed.

Remove Care-Ally Arm

Those enrolled in the CAM arm who the study team enrolled without an ally with the intent of pairing them with a Veteran volunteer will receive four incentive massages in lieu of the CAM arm. They will be reconsented on a new form prior to this. They will also be invited to the single MT self-care session with [name] after reconsenting, which will consist of the self-care components of the CAM class.

Current CAM participants who have not yet attended a class will have three months to attend the class before it is discontinued. Serious effort will be made to reach these participants and notify them.

Current CAM participants who have already continued the class will continue as normal.

Incentive CAM Class: TTM and WLC Participants consented on the new form will be welcome to attend the new incentive class that replaces the CAM arm. It will consist of all the self-care portions of the CAM class. Participants consented on the pre-modification form will have access to the incentive CAM class, to maintain the protocol they were consented with initially. The last incentive CAM class will be held 9 months after the amendment is approved (giving participants a three month buffer to attend).

6.0 Reporting of Adverse Events or Unanticipated Problems involving Risk to Participants or Others

We follow local IRB guidelines for reporting adverse events. These include:

- Upon becoming aware of a death of an enrolled TOMCATT participant, which was both unanticipated and related to the research, the study team will immediately notify the IRB via verbal notification. If required, a written notice to the IRB will be submitted within 5 business days following the event

For additional oversight of massage application safety and to pre-emptively address potential concerns, [name] and massage assistants will review all treatment related notes (TT-M arm) daily

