1.0 Background

Data from the 2012 National Health Interview Survey indicate that during a 3-month period, 15% of adults reported neck pain. The 12-month prevalence of chronic neck pain is estimated to be between 30%-50%. Neck pain is especially common in adults older than 50 years and is the fourth leading cause of disability in the United States, after back pain, depression, and joint pain. In a 2008 VA study, Dobsha et al. found back and neck pain diagnoses were present in 67% of 401 Veterans. In another VA study, the two most common cervical spine diagnoses were stenosis (50%) and disk herniation (23%). In Veterans with these diagnoses, neck pain was reported by 96%. The impact of chronic neck pain is widespread, exerting negative effects on individuals' physical, psychological, and economic well-being. Chronic neck pain reduces functional status, quality of life, and is associated with deleterious psychological outcomes, including depression and anxiety. Chronic neck pain is a major reason for health care utilization, accounting for more than 10 million ambulatory medical visits per year. The economic impact of this utilization is significant.

Guidelines highlight a wide range of treatment options for chronic neck pain. In clinical practice, conventional treatments such as medications and physical therapy are most widely used. However, systematic reviews conclude there is still limited evidence for the effectiveness of these treatments for neck pain, relative to low back pain, and current therapies show only modest effect sizes. The mainstay of chronic neck pain treatment is non-steroidal anti-inflammatory drugs (NSAIDs), but NSAIDs often provide suboptimal pain relief, especially when used as mono-therapy, and their adverse effects, such as gastrointestinal, renal, and cardiovascular complications, are well known. Opioids for chronic neck pain are controversial for several reasons. First, their long-term efficacy is questionable. Second, opioids are associated with several problematic side effects. Third, opioids have potential for misuse, abuse, and addiction. Fourth, between 1999 and 2008, the rate of prescription opioid overdose deaths in the US raised four-fold. Thus, when medications and physical therapy fail to relieve pain, Veterans frequently live with chronic, often debilitating, pain. Clearly, effective and safer treatments to improve the management of neck pain are needed.

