Since this study is not specifically powered for secondary outcomes, these results should be interpreted cautiously. Pain intensity, pain interference, health-related quality of life (HRQL), depression, anxiety, and pain cognitions are all continuous measures. These subscales will be analyzed with the same approach as the primary outcome. For the pain intensity score, we will also report a clinically relevant descriptive statistic in which we define patients with > 30% reduction from baseline as "responders." For the NDI, a "responder" will be defined as a decrease of more than 5 points from baseline. This binary outcome will be observed at 1, 3, and 6 months (pre A033 only) for each participant. A generalized linear mixed model with predictors of group, time, and their interaction will be used that also includes a random subject effect to accommodate the potential correlation among observations from the same participant. The primary contrasts of interest will be the difference in proportions at 3 months between each treatment and the control group. We will use the Šídák method to adjust for multiple comparisons. Differences in proportions between treatment groups at the other time points will also be reported. For exploratory measures regression models will be used based on data type and will include pain coping, sleep problems, satisfaction, and social support.

Moderator analyses

As a secondary analysis for the primary outcome (NDI) as well as secondary outcomes, we will test baseline anxiety (GAD-7 and PTSD) and depression (PHQ-9) as moderators. This will be done separately for each potential moderator by re-running each mixed model for primary and secondary outcomes while additionally including the moderator, the moderator by treatment group interaction, and the moderator by treatment by time interaction. The treatment by time by moderator interaction represents the moderation effect on the treatment difference. If the treatment term is significant then moderation is occurring. Testing these measures as moderators will provide insight into generalizability of the interventions. For example, if the intervention loses effect in patients with high anxiety or depression, these patients may not be suited to the intervention.

Missing data

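### Adverse events are not sought in the same way in both arms, and no between-arm analysis of adverse events or of the share made worse is prespecified

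*Combined protocol and SAP*

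**What the plan says.** **How events are found.** Section 6.0 opens with "We follow local IRB guidelines for reporting adverse events". The one reporting rule visible there begins "Upon becoming aware of a death of an enrolled TOMCATT participant, which was both unanticipated and related to the research". The daily review of TT-M notes is then introduced with "For additional oversight of massage application safety and to pre-emptively address potential concerns", and the text goes on to say that "massage assistants will review all treatment related notes (TT-M arm) daily". On what the therapists write down, Section 5.0 says "the therapists will document treatment delivery details (techniques, time) with online, REDCap forms"; it names no adverse-event field. The adherence paragraph for TT-M adds that patients are encouraged to telephone staff about problems. Section 7.0 has staff establish why any patient withdraws, and treatment side effects is one of the possible reasons.

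**What is measured in both arms.** Under the waitlist heading in Section 5.0: "Participants in the control arm will undergo outcome assessments on the same schedule". Table 2 places the NDI, Brief Pain Inventory, PROMIS pain interference and global impression of change at baseline, 1, 3 and 6 months (6 months only for those enrolled before A033). It also schedules mood and somatic symptom scales. It lists no adverse-event item.

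**What is analysed.** Section 8.0 compares mean NDI change between arms in a mixed model, with the main contrast at 3 months, and treats the continuous secondary outcomes the same way. An NDI responder "will be defined as a decrease of more than 5 points from baseline". A pain responder needs a reduction of more than 30%. Neither definition has a counterpart for worsening, and no adverse-event table is planned.

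**The concern.** If events come to light mainly through treatment notes, the count in TT-M has no comparator. A flare after massage cannot then be separated from the ordinary fluctuation of chronic neck pain, and a new event such as an injury or an admission is more likely to be recorded in the arm that is seen often.

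Separately, a mean difference in NDI can favour massage while some patients get worse. A responder rate that counts only improvement puts those patients in the same category as patients who did not change.

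Section 1.0 argues that "effective and safer treatments to improve the management of neck pain are needed". A trial introduced that way will be asked what it found about harm, and the plan prepares no between-arm answer.

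**Working it through.** **1. Sources set side by side**

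| Source of harm information | TT-M | WL-C | By-arm analysis planned |
|---|---|---|---|
| Daily review of treatment notes (6.0) | yes | none generated | no |
| Encouragement to call staff (5.0, TT-M adherence) | yes | not stated | no |
| Withdrawal reasons (7.0) | yes | yes | none stated |
| NDI, pain, global change (Table 2) | yes | yes, same schedule | mean NDI and pain change; improvement-only responder rates |
| Adverse-event question (Table 2) | none | none | no |

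The symptom scales are symmetric; the event sources are not.

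**2. The plan's own sample size**

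Inputs from Section 8.0: 0.4 SD, Type I error 0.05, 80% power, 1:1 allocation.

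- n per arm = 2 × (1.96 + 0.8416)² / 0.4² = 2 × 7.849 / 0.16 = 98.1, so 99; the exact t-test gives 99.1, so 100. The stated 100 per group reproduces (two-sided).
- Inflation: 200 / 0.76 = 263.2, so 264; 264 + 32 = 296. Both reproduce.

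Neither proposed change alters these figures.

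**3. Precision for the proportion worsened**

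The documents give no worsening rate, so q (the rate in each arm) is assumed. With 100 completers per arm, half-width = 1.96 × √(2q(1−q)/100).

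- q = 0.05: 1.96 × √0.00095 = 0.060
- q = 0.10: 1.96 × √0.00180 = 0.083
- q = 0.15: 1.96 × √0.00255 = 0.099

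That is about 6, 8 and 10 percentage points.

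**4. Power for an excess in TT-M**

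Two-sided 0.05, 100 per arm, normal approximation with pooled variance under the null. For 10% against 25%: the mean proportion is 0.175, and z = (0.15 × √100 − 1.96 × √(2 × 0.175 × 0.825)) / √(0.10 × 0.90 + 0.25 × 0.75) = (1.500 − 1.053) / 0.527 = 0.85, giving power of 0.80. Other assumed control rates:

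| Control rate | TT-M rate for 80% power | Excess | Power, 10-point excess | Power, 5-point excess |
|---|---|---|---|---|
| 5% | 17.5% | 12.5 points | 66% | 27% |
| 10% | 25% | 15 points | 51% | 19% |
| 15% | 31.7% | 16.7 points | 42% | 15% |
| 20% | 37.9% | 17.9 points | 37% | 13% |

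Only an excess of about 12 to 18 points would be detected reliably. The comparison should be reported as an estimate with an interval, not as a test.

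**The case against.** Several stronger readings are tempting, and the documents do not support them.

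- *Harm is never measured in the waitlist arm.* Table 2 and the waitlist paragraph put the same symptom scales in both arms, and Section 5.0 says that medication use and specialist consultations for neck pain are assessed in order to adjust for differences between arms. Withdrawal reasons cover both arms, although they reach only patients who leave and side effects of study treatment have no waitlist counterpart.
- *Nothing is measured after the last massage.* The 3-month assessment is the immediate post-intervention one, and patients enrolled before A033 are also assessed 3 months later. Only later enrollees have no assessment beyond 3 months.
- *The trial cannot say whether massage makes patients worse.* Mean NDI and pain changes are compared by randomised arm, and the share worsened can be derived from data already scheduled. What is missing is the prespecified summary.
- *Up to 24 notes against none measures the bias.* The 24 follows from 18 visits being 75%, but untreated patients have no treatment notes, so the contrast measures nothing.
- *Note review is the whole safety system.* The plan presents it as an addition to local IRB guidelines, which are not reproduced. Section 6.0 announces a list and shows one item, so text may have been lost; absent reporting rules should not be counted against the plan. Reporting an event is still a different matter from finding one, and Table 2 and Section 8.0 show what is collected and analysed.

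It is also fair to say that no aim in Section 2.0 tests safety, and that the background calls massage safer than drugs, which a waitlist comparison cannot test. That limits what is at stake. It does not remove the gap in harm reporting.

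**Conclusion.** The point holds in limited form. The visible plan has no systematic adverse-event ascertainment applied equally to both arms. It prespecifies no between-arm analysis of adverse events, nor of the proportion of patients who worsen. Mean worsening is compared, and the primary efficacy inference is untouched.

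At 100 completers per arm, the missing worsening comparison would carry a half-width of about 6 to 10 points for assumed rates of 5% to 15%, with 80% power only for an excess of about 12 to 18 points at assumed control rates of 5% to 20%. Those rates are illustrative. The figures apply at 3 months if the planned number of completers is reached; precision at 6 months will be lower if fewer than 100 per arm are assessed, since only pre-A033 enrollees contribute. The conclusion also rests on the text as available, including the possibly incomplete list in Section 6.0.

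**What to change.** 1. **Section 8.0, secondary outcomes.** Add the proportion with an NDI increase of more than 5 points from baseline, by arm, at 1, 3 and (pre-A033) 6 months, as a difference with a 95% confidence interval. Specify it before anyone examines between-arm data, and label it descriptive because of the limited power. Cost: one table from data already collected, covering every patient already assessed.

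2. **Table 2 and Section 6.0.** For assessments still to come, put one identically worded adverse-event question to both arms at the existing time points. Tabulate events by arm from that source only, and report events found in therapist notes separately, as uncontrolled TT-M data. Cost: one or two minutes per assessment and a form amendment.

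The second change has a drawback. Section 8.0 already reports about 100 patients per group, so many assessments will have been done without the question. Its table must be restricted to assessments at which the question was asked in both arms, with those denominators shown. More minor events will also be logged. Neither change affects sample size, randomisation, treatment or the primary analysis.

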7.0 Study Withdrawal/Discontinuation

Subjects will be allowed to withdraw from the trial at any time. If a patient withdraws, we will determine the reason for withdrawal. Possible reasons will include: 1) death, 2) worsening of comorbid medical conditions making follow-up impossible, 3) treatment side

effects, and 4) other. If subjects withdraw, we will attempt to obtain their permission to complete the remaining outcome assessments. Data will be analyzed on an intent-to-treat basis.

Subjects will be removed from the TT-M intervention but allowed to continue in the study (data collection and incentives) if they a) fail to show-up or notify study personnel for the need to reschedule three times during the three month intervention period or b) demonstrate inappropriate conduct (i.e., sexual advancement, expectation, or harassment).

8.0 Statistical Considerations

Sample size and power

The TOMCATT RCT was 'paused' on enrollment, study assessments, and massages in the TTM arm (massage arm) during an almost one year time period due to underlying safety concerns of trying to provide the intervention during the COVID-19 pandemic, although the control group was only 'paused' on enrollment. This impacted 16 patients enrolled in the TTM arm, of which 8/16 had completed their 1 Month assessment. The study will now be 'unpaused' for all, in which case new patients will be randomized and enrolled to the two study arms.

The primary intention-to-treat analysis will include all participants randomized and all assessments collected prior to pause for the TTM and all assessments for the waitlist control arm. Data will be analyzed as in the original analysis plan assuming data collection points were collected at TRT END and FOLLOW-UP on same time schedule (baseline, 1M, 3M, and 6M). Since 16 subjects were paused on their treatments and it has been over a year since they received a massage, for the primary analysis these patients will be considered lost-to-follow-up. Thus, we will recruit additional subjects to account for the increased LTF rate over what was originally expected due to COVID-19.

Original modification sample size: The modified study will focus on comparison of the TT-M and the waitlist control group (WL-C). We need 100 patients per group ($N = 200$) by 3 months to have 80% power to detect a 0.4 SD difference in change in NDI from baseline between TT-M and control with Type I error = 0.05 for the comparison of interest: TT-M vs WL-C. All analysis will be conducted under the intention-to-treat principle. Sample size was derived based on an independent two-sample t-test which is conservative compared to the contrast from our proposed linear mixed model.

Assuming total attrition for the TTM and WL-C arm is $(27+20)/(98+99) = 47/197 = 24\%$, we will seek to enroll a Total $N = 264$ ($200/.76$) or 132 per group in the TT-M and WL-C study groups. As we already have approximately 100 per group, with our current recruitment rate of 12 per month, we should be able to enroll an additional 64 subjects over 6 months.

New modification sample size: For the comparison of the TT-M and the waitlist control group (WL-C) we need 100 patients per group ($N = 200$) by 3 months to have 80% power to detect a 0.4 SD difference in change in NDI from baseline between TT-M and control with Type I error = 0.05 for the comparison of interest: TT-M vs WL-C. All analysis will be conducted under the intention-to-treat principle. Sample size was derived based on an independent two-sample t-test which is conservative compared to the contrast from our proposed linear mixed model.

Previously we assumed a total attrition for the TTM and WL-C arm of $(27+20)/(98+99) = 47/197 = 24\%$, thus we sought to enroll a Total $N = 264$ ($200/.76$) or 132 per group in the TT-M and WL-C study groups. We will now enroll Total $N = 296$ ($264 + 16 \times 2$) so that we will

have an additional 16 in the TTM arm to account for the 16 that were paused due to COVID but will also maintain the current randomization allocation. For IRB purposes, we will continue to recruit to reach at most N = 308 this would increase the 16 COVID paused to also account for potential 24% attrition (16/.76 = 22 per group). However, this is not necessarily required as the COVID paused will still be included in the linear mixed model up until their one month assessment. This should allow us to reach our sample size of 100 per group to complete the 3 month assessment.

Data analysis: Baseline characteristics of TOMCATT sample

As an RCT, we expect characteristics of study participants to be balanced across the two study arms. We will compare all baseline demographic and clinical characteristics between the treatment groups using the appropriate test (ie, ANOVA, Kruskal-Wallis test, or Chi-square test). Variables found to significantly differ will be included in subsequent regression models.

Main analysis (Aim 1) of the primary outcome (NDI total score)

All outcomes will be collected at baseline, 1, 3, and 6 months. Six-month outcomes will only be collected for those who consent prior to approval of A033. For the primary outcome of Neck Disability Index (NDI) total score, we will use a linear mixed effect model with an appropriate covariance structure to compare the treatment arm to the control arm on rate of change as well as difference in outcome at the 3-month time point. Fixed effects will include treatment, time (as categorical), and treatment by time interaction. Difference in amount of change in outcome between groups at the other time points (1 and 6 months (pre A033 only)) will also be estimated and reported. We will examine the associations among the repeated measures within subjects and use a data driven approach in determining the appropriate variance-covariance structure.⁷¹ We will use the Šídák method to adjust for multiple comparisons. All analyses will include checking of assumptions and model fit. We plan intent-to-treat with the primary endpoint at 3 months and evaluation of "early" response at 1 month and "sustained" response at 6 months post-randomization (pre A033 only).

Analysis of secondary outcomes (Aim 2)

Since this study is not specifically powered for secondary outcomes, these results should be interpreted cautiously. Pain intensity, pain interference, health-related quality of life (HRQL), depression, anxiety, and pain cognitions are all continuous measures. These subscales will be analyzed with the same approach as the primary outcome. For the pain intensity score, we will also report a clinically relevant descriptive statistic in which we define patients with > 30% reduction from baseline as "responders." For the NDI, a "responder" will be defined as a decrease of more than 5 points from baseline. This binary outcome will be observed at 1, 3, and 6 months (pre A033 only) for each participant. A generalized linear mixed model with predictors of group, time, and their interaction will be used that also includes a random subject effect to accommodate the potential correlation among observations from the same participant. The primary contrasts of interest will be the difference in proportions at 3 months between each treatment and the control group. We will use the Šídák method to adjust for multiple comparisons. Differences in proportions between treatment groups at the other time points will also be reported. For exploratory measures regression models will be used based on data type and will include pain coping, sleep problems, satisfaction, and social support.

Moderator analyses

As a secondary analysis for the primary outcome (NDI) as well as secondary outcomes, we will test baseline anxiety (GAD-7 and PTSD) and depression (PHQ-9) as moderators. This will be done separately for each potential moderator by re-running each mixed model for primary and secondary outcomes while additionally including the moderator, the moderator by treatment group interaction, and the moderator by treatment by time interaction. The treatment by time by moderator interaction represents the moderation effect on the treatment difference. If the treatment term is significant then moderation is occurring. Testing these measures as moderators will provide insight into generalizability of the interventions. For example, if the intervention loses effect in patients with high anxiety or depression, these patients may not be suited to the intervention.

Missing data

We expect missing data in two different forms: missing by attrition and intermittent missing of observation. Attrition of < 15% is expected at the 3-month follow-up. We do not expect differential attrition between study arms. We will examine effects of missing observations due to attrition by examining patient characteristics associated with dropout. Factors associated with intermittent missing can similarly be identified. If missing data appears to be unrelated to any observed patient characteristics, and there are no obvious reasons to believe they are related to any unobserved characteristics, we will analyze the data under the assumption of missing completely at random (MCAR). If examination reveals observed factors are related to data missing, we will analyze data under the assumption of data missing at random (MAR). Multiple imputation techniques will be used to alleviate the impact of missing data. Importantly, the proposed mixed model methods for longitudinal data are appropriate if data are MCAR or MAR. However, if the pattern of missing data is nonignorable, more complex modeling approaches that model the missing data mechanism based on the EM algorithm or pattern-mixture models that include variables defined by the subject's pattern of missing data may be used. Finally, we will conduct sensitivity analyses to ensure the validity of study findings.

Data Collection for Aim 3

Aim 3 will examine the intervention implementation potential, including facilitators and barriers, and adherence, and intervention costs. Findings from this aim will help to maximize implementation potential and shorten the timeline to implementation in VA clinical settings.

Participants for Qualitative Interviews

For Veterans, the Aim 3 interviews will be conducted after the 3-month outcome assessment. We will purposefully sample Veterans with wide variations in change in pain disability (NDI total) from baseline to the 3-month assessment, and intervention adherence (e.g., number of massage sessions during the intervention period). Analysis will occur in parallel with data collection to allow sampling to theoretical saturation (i.e., no new properties, dimensions, or other qualities are seen in the data). Based on our experience and recommendations for qualitative sampling of subgroups, we expect to conduct up to 36 interviews.

Qualitative Interviews

The staff members will conduct the interviews. Interviews will last approximately 45-60 minutes and will be tailored to each respondent's role. Development of the interview guide is informed from our previous qualitative work questions will be further developed, revised, and piloted prior to beginning interviews. Interview questions will focus on perceptions of barriers and facilitators to using massage therapy and whether the massage interventions were helpful/valuable or not and why. Interviews will be audio-recorded and transcribed. Interview responses will help guide the next study as we plan for implementation while simultaneously evaluating, and working to maximize, effectiveness. We have found qualitative work like this to be highly informative in elucidating trial results.

Qualitative Data Analysis for Aim 3 Interviews

[name] will lead the qualitative analysis, which will occur in two broad phases: open coding and focused coding. Open coding facilitates development of a code list for further analysis. In this phase, two experienced qualitative data analysts ([name]) will independently read through selected transcripts to gain a general understanding of the data and variation across participants. Then, analysts will independently label each line of data with initial codes, or categories that reflect meanings or themes emerging from the text, and meet to discuss these interpretations. This will occur iteratively until analysts agree on emergent thematic categories (codes). In phase 2, focused coding, all transcripts will be divided evenly among analysts, who will apply the codes derived in the first analytic phase to assigned transcripts. A subset of transcripts will be coded by all analysts and discussed to ensure consistency in coding, with discrepancies resolved by consensus. NVivo 10 will facilitate data management and analysis.

Intervention costs

We will use both micro- and gross costing methods to estimate intervention costs. Applying VA Health Economics Resource Center (HERC) guidelines, we will measure intervention-related activities and their associated costs. These intervention costs will include: 1) massage therapist average salaries plus fringe; 2) study materials (DVDs, manual) provided to intervention patients; 3) parking; 4) facility overhead; and 5) professional time required for care ally - assisted massage training and supervision. These costs will allow us to calculate the cost of professional time per Veteran patient across the treatment arms. Costs will be reported in current year's dollars. Sensitivity analyses will be used to account for assumptions, including changes in intervention costs. If the treatments are found to be differentially more effective, we will perform a cost-outcome analysis (i.e., incremental cost-effectiveness). We will estimate the effect of the massage on the primary outcome (NDI). The incremental cost to achieve a clinically meaningful decrease in NDI due to massage, i.e., the cost-effectiveness ratio, is calculated as the difference in intervention costs between the two treatment arms, divided by the difference in effectiveness between groups. This data will provide useful information to VA administrators and managers about the short-term budget implications of implementing each of the interventions.

